12.1.7 Number of Subjects with Any Grouping Adverse Event

The occurrence of AEs will be summarized by any grouping Adverse Event, preferred term according to the MedDRA dictionary, and by ethnic background and by severity. Grouping Adverse Event is following.

Grouped Term	Preferred Terms
Fatigue/malaise	Fatigue, Malaise
Hepatic function test abnormal	Aspartate aminotransferase increased, Alanine aminotransferase increased, Gamma-glutamyltransferase increased
Anaemia	Anaemia, Haemoglobin decreased
Thrombocytopenia	Thrombocytopenia, Platelet count decreased
Neutropenia	Neutropenia, Neutrophil count decreased
Lymphopenia	Lymphopenia, Lymphocyte count decreased
Leukopenia	Leukopenia, White blood cell count decreased
Injection site reaction	Infusion site pain, Injection site pain, Injection site reaction, Injection site rash, Infusion site pruritus, Infusion site rash
Hyperglycaemia	Hyperglycaemia, Blood glucose increased
Taste disorder	Taste disorder, Dysgeusia
Hyperbilirubinaemia	Hyperbilirubinaemia, Blood bilirubin increased
Hypoalbuminaemia	Hypoalbuminaemia, Blood albumin decreased
Hypomagnesaemia	Hypomagnesaemia, Blood magnesium decreased
Hyponatraemia	Hyponatraemia, Blood sodium decreased
Hypokalaemia	Hypokalaemia, Blood potassium decreased
Catheter site related reaction	Catheter site pain, Catheter site related reaction, Catheter site haemorrhage, Catheter site erythema, Catheter site bruise, Catheter site pruritus, Catheter site rash, Catheter site oedema, Catheter site discharge, Catheter site swelling
Abdominal pain	Abdominal pain, Abdominal tenderness, Abdominal pain lower, Abdominal pain upper
Sepsis/Bacteraemia	Sepsis, Bacteraemia, Enterococcal bacteraemia, Escherichia sepsis, Pseudomonal sepsis, Device related sepsis, Neutropenic sepsis, Staphylococcal bacteraemia

Grouped Term	Preferred Terms
Neuropathy peripheral	Neuropathy peripheral, Peripheral sensory neuropathy

12.1.8 Number of Subjects with Any Grouping Adverse Drug Reaction

The same analyses described in 12.1.7 will be performed for Adverse Drug Reaction.

12.2 Laboratory/ECG/Vital sign Parameters Evaluation

12.2.1 Summary of Laboratory Parameters

Descriptive statistics of hematologic/biochemical/blood coagulation test parameters specified in the following table will be calculated by time point for both of measured values and changes from baseline.

If laboratory test value is less than or equal to detection limit value, the value is treated as detection limit value.

Hematological test parameters	Hemoglobin, Hematocrit, Red blood cell (RBC) count, White blood cell (WBC) count, Differential leukocyte count (Band Neutrophils, Segmented Neutrophils, Neutrophils, Lymphocyte, Monocyte, Eosinophil, Basophil), Platelet count
Biochemical test parameters	Sodium (Na), Potassium (K), Chloride (Cl), Calcium (Ca), Aspartate aminotransferase (AST), Alanine aminotransferase (ALT), Alkaline phosphatase (ALP), Lactic dehydrogenase (LDH), Total bilirubin, Total protein, Albumin, C-reactive protein (CRP), Creatinine, Blood urea nitrogen, Uric acid, Glucose
Blood coagulation test parameters	Prothrombin time-INR (PT-INR), Prothrombin time (PT), Activated partial thromboplastin time (APTT)

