5.4.3. Study Discontinuation Criteria

If a subject meets any of the following criteria before the start of dosing in each cycle from Cycle 2, the subject will discontinue (not continue) the study without starting the investigational drug administration in the next cycle:

- (1) PD or RD at the tumor response assessment [See Section 6.14.2]
- (2) Clinical judgment of “symptomatic progression” by the principal investigator or sub-investigator; based on clinical symptoms or laboratory findings, etc., in case of no results of radiological assessment with PET/CT image data
- (3) Start of treatment with proscribed concomitant drugs or therapies [See Section 5.5.2]
- (4) A Grade 4 AE that is related to the investigational drug

In case of the transient changes in laboratory test values without any clinically significant symptoms; e.g., the severity of changes in laboratory test values has recovered to “≤ Grade 2” within 7 days, the investigational drug administration will be continued at the discretion of the principal investigator

- (5) No improvement in the severity of an AE that is related to the investigational drug to “≤ Grade 1” or “Grade at pretreatment”

The start of next cycle can be postponed for up to 3 weeks to allow the investigational-drug-related AE to be resolved. If the AE is not resolved to “≤ Grade 1” or “Grade at pretreatment” even though the start of next cycle is postponed for 3 weeks, the subject will complete the study after the completion of the examinations, observations and investigations scheduled during the follow-up period.

- (6) No resolution or relapse of a similar investigational-drug-related AE at ≥ Grade 3 despite a dose reduction of the investigational drug [See Section 5.4.2]

However, the subject may continue receiving the investigational drug at a reduced dose at the discretion of the principal investigator, in case that the subject shows the response to the investigational drug; i.e., the tumor response in the subject is not assessed as PD or RD.

- (7) The principal investigator or sub-investigator decision not to continue investigational drug administration due to the occurrence of an investigational-drug-related AE, other than the events defined in (4), (5), and (6) above or other reasons.

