6. STUDY PROCEDURES

The principal investigator or sub-investigator (or designated staff) will enter the results of examination, observation and investigation specified in this Section 6, and also the dates and times for blood and urine collection, as needed, into the eCRF.

The frequent performance of such invasive examinations and medical imaging tests; such as bone marrow biopsy and CT/PET imaging test, are considered medically and ethically unfavorable. Therefore, the bone marrow biopsy, CT and PET data that are obtained from routine medical practice before obtaining the informed consent from the subject may be allowed to be used as screening data of this study; only when these invasive examinations and medical imaging tests are performed within 28 days before subject enrollment. For the use of such data, a prior consent from the subject is required. However, PET data should be taken according to the study-specific procedures that is standardized by the Central Imaging Review institution of this study.

The principal investigator or sub-investigator will be allowed to add the time points of examinations, observations and investigations as needed for the follow-up observation of AEs.

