7. SAFETY DATA COLLECTION AND REPORTING

7.1. Definitions

7.1.1. Adverse Events

An adverse event (AE) is defined as “any untoward medical occurrence in a subject administered an investigational drug and which does not necessarily have a causal relationship with this treatment”.

This definition of AEs includes any such medical occurrences or exacerbation of pre-existing medical conditions or events (primary disease, underlying disease or concurrent diseases etc.). Obvious exacerbation of the pre-existing medical conditions; worsening in severity, increase in frequency, or extending of duration of the events, in the judgment of the principal investigator or sub-investigator, will qualify as an AE.

The principal investigator or sub-investigator will identify a “term” of diagnosis or syndrome of the AE as much as possible. Diseases or clinical signs with accompanying symptoms, the diseases or clinical signs will be identified and qualified as AEs.

The principal investigator or sub-investigator is responsible to confirm the changes in laboratory test results (vital signs, ECGs, laboratory test values, etc.) from baseline values in an individual subject. The clinically significant abnormal changes; including any change for which a new treatment or alternative treatment, in the judgment of the principal investigator or sub-investigator, will qualify as AEs. Diseases or clinical signs accompanying abnormal laboratory findings, the diseases or clinical signs will qualify as AEs.

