7.2. Procedures for Adverse Events Reporting

The principal investigator or sub-investigator (or designated staff) will collect and identify the following information on AEs during the period from the start of investigational drug administration to the end of follow-up period, and enter a description of the event into the eCRF.

- Term of adverse event
- Date of onset
- Seriousness; serious or not serious
- Severity
- Relationship to the investigational drug; if “No,” the reason for “No”
- Any action taken; if “Yes,” the details of the action
- Outcome and date of outcome confirmation (date of resolution, date of confirmation or examination of resolving/not resolved events, date of death, etc.)

Relationship (Causality)

Relationship of an AE to the investigational drug should be assessed from the point of view that “there is a reasonable possibility that the investigational drug caused the AE”. The principal investigator or sub-investigator should determine either of “Yes” or “No”.

Severity Assessment

Severity of an AE will be assessed by the principal investigator or sub-investigator, using the 5-grade scale according to NCI-CTCAE Version 4.0. For those events not found in NCI-CTCAE Version 4.0, the principal investigator or sub-investigator will clinically determine the severity based on the definition in Table 13.

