9.4.4. Analysis of Safety Endpoints

The incidence of AEs will be summarized by system organ class and by preferred term according to the ICH-MedDRA, and by ethnic background and severity. Incidence of investigational-drug-related AEs, serious AEs (SAEs) and investigational-drug-related SAEs will be also summarized, respectively, in the same way.

SAEs, SAEs of \geq Grade 3, and significant AEs in the judgement of the Development Sponsor; e.g. neurological disorder and psychiatric disorder, will be summarized or described.

Vital signs, laboratory values and ECG parameters will be summarized by item and time point.

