7.2 Descriptive Statistics

Following descriptive statistics will be summarized.

- Continuous variables
 - Number of available data, Mean, Standard deviation (SD), Median, First and third quartile points, Minimum and Maximum
- Categorical variables
 - Frequency and Percentage

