12.1.2 Number of Subjects with Any Adverse Event

The occurrence of AEs will be summarized by system organ class and by preferred term according to the Medical Dictionary for Regulatory Activities (MedDRA) dictionary, and by ethnic background (Japanese, Except Japanese, Korean, Taiwanese, Hong Konger/Chinese and others) and by severity.

The bar graph will be produced to show the occurrence of AEs by severity.

When one subject experiences same PT of AE more than once, the severest event will be counted (National Cancer Institute Common Terminology Criteria for Adverse Events [NCI-CTCAE] Grade 1 < Grade 2 < Grade 3 < Grade 4 < Grade 5). Adverse event of NCI-CTCAE Grade 3 or higher will be also summarized in the same way.

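### No planned table shows how many subjects ever reached Grade 3-4 on measured laboratory values: laboratory data are summarised by time point, and the graded tables count only changes that investigators reported as adverse events

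*SAP*

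**What the plan says.** **Measured values.** SAP 12.2.1: "Descriptive statistics of hematologic/biochemical/blood coagulation test parameters specified in the following table will be calculated by time point for both of measured values", and also for changes from baseline. SAP 7.2 lists the statistics for continuous variables: "Number of available data, Mean, Standard deviation (SD), Median, First and third quartile points, Minimum and Maximum". Protocol 9.4.4 agrees: "Vital signs, laboratory values and ECG parameters will be summarized by item and time point".

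**When a laboratory change is an AE.** Protocol 7.1.1 limits this to "The clinically significant abnormal changes; including any change for which a new treatment or alternative treatment, in the judgment of the principal investigator" or sub-investigator.

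**Grading.** Protocol 7.2 has the investigator assess the severity of AEs "using the 5-grade scale according to NCI-CTCAE Version 4.0". SAP 12.1.2 tabulates AEs by severity and adds: "Adverse event of NCI-CTCAE Grade 3 or higher will be also summarized in the same way". SAP 12.1.7 groups laboratory preferred terms with their clinical equivalents, for example for neutrophils, platelets and haemoglobin, again by severity of the reported AE.

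**Elsewhere.** The SAP's only shift tables are for neurological and mental status (12.2.2). Individual laboratory results appear in the listings (SAP 13).

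**The concern.** Safety is the first secondary objective, and Appendix 2 of the protocol calls the drug a cytotoxic antitumor drug. A reader of the study report will want to know how many subjects had a severe fall in neutrophils or platelets, or a severe rise in transaminases. As planned, that number can come only from AE reports. The study is open-label and single-arm, runs in several countries and regions, and leaves it to each investigator whether a laboratory change is clinically significant. If investigators apply that test differently, the reported rates differ for reasons unrelated to the drug, including in the AE tables split by ethnic background. The measured values are in the database and would give a count that does not depend on this judgement, but no table uses them that way.

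**Working it through.** The plan states no figure for laboratory toxicity, so there is none to reproduce. The check has three steps.

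**1. Is there a count from measured values anywhere?**

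| Output | Unit shown | Source of grade |
|---|---|---|
| SAP 12.2.1, Protocol 9.4.4 | values at each time point | none |
| SAP 12.1.1 to 12.1.8 | subjects with an AE | investigator's AE grade |
| SAP 12.2.2 (shift tables) | neurological and mental findings | not laboratory |
| SAP 13 (listings) | individual results | none planned |

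No row gives subjects by grade of measured laboratory value.

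**2. Can the count be recovered from by-visit statistics?** Take 65 subjects and two visits. At each visit the values are 0.6, 0.8, 0.9 and 62 equally spaced values from 1.6 to 7.0. The cut-off of 1.0 is arbitrary. Every visit then shows n 65, mean 4.14, SD 1.73, median 4.17, quartiles 2.75 and 5.58, minimum 0.6 and maximum 7.0.

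- The same three subjects are low at both visits: 3 subjects are ever below the cut-off.
- A different three are low at the second visit: 3 + 3 = 6.

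The summaries of measured values are identical in both cases. If all subjects also share one baseline value, each change is the value minus a constant, so the change summaries are identical too. The by-visit tables therefore do not determine the count.

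**3. How far apart can the visit rate and the ever rate be?** The number of draws follows from Protocol Table 5: 3 in Cycle 1 after the first dose (Days 5, 8, 15), 3 in each of Cycles 2 to 6 (Days 1, 8, 15) and 1 at follow-up, so 3 + 5 × 3 + 1 = 19. Protocol Tables 10 to 12 agree: 5 + 5 × 3 + 1 = 21 draws, less the screening and Cycle 1 Day 1 pre-dose draws, is 19.

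Let p be the chance of a Grade 3 or higher value at one draw. The documents do not give p, so a range is assumed, with every subject completing six cycles and all draws. If the same subjects are affected every time, the share ever affected is p. If draws are independent, it is 1 − (1 − p)^19.

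| Assumed p per draw | Same subjects every time | Independent draws |
|---|---|---|
| 1% | 1% | 1 − 0.99^19 = 17% |
| 2% | 2% | 1 − 0.98^19 = 32% |
| 5% | 5% | 1 − 0.95^19 = 62% |

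Values within a subject are likely to be correlated, so the truth would normally lie between the two columns. The table shows how little a visit rate says about the ever rate. It is not a forecast for this trial.

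**The case against.** The other side has several good points.

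- **Severe values are not hidden.** A reader might infer that averages bury the severe falls. SAP 7.2 includes the minimum and quartiles, so an extreme value at a visit will print. This stands: what is missing is the number of subjects.
- **The AE tables carry much of the information.** They give subject counts by preferred term and grade, and SAP 12.1.7 merges the laboratory terms. In the two phase 1 PTCL studies, Grade 3 or higher related neutrophil and platelet decreases were each reported as AEs in 2 of 23 subjects, so the AE route does pick up such events. It is still limited to what was reported.
- **Under-reporting is not shown.** A reader might infer that the AE rates must be biased downward. Protocol 5.4.3 item (4) makes an exception to the discontinuation criterion for a related Grade 4 AE: "In case of the transient changes in laboratory test values without any clinically significant symptoms". That exception would have little use unless some asymptomatic laboratory changes were recorded as graded AEs. Understatement is possible, but the documents establish neither that it occurs nor how large it is.
- **Unscheduled results.** A reader might infer that these are excluded, or that they hold the worst values. Protocol Section 6 says only that investigators "will be allowed to add the time points of examinations, observations and investigations as needed for the follow-up observation of AEs". Such tests follow an AE that should already be recorded, and SAP 12.2.1 states no rule for them. Neither inference is supported. The absence of a rule is a reason to state one.
- **Treatment rules.** The skip, reduction and discontinuation criteria in Protocol 5.4 that refer to grade concern drug-related AEs. A grade table from raw values would not reproduce those triggers and should not be justified on that ground.
- **No contradiction, and recoverable later.** SAP 12.2.1 agrees with Protocol 9.4.4, the safety endpoint is occurrence of AEs, and the count could be derived from listed data. That is true, but a display chosen after the data are seen is weaker than one specified in advance.

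**Conclusion.** The point holds as a moderate reporting gap that is cheap to close. Neither document plans a per-subject count of Grade 3-4 laboratory values based on the measurements, and the planned by-visit statistics cannot supply one. The stated rate of severe laboratory toxicity will rest on which changes investigators judged clinically significant. It may be too low. The documents give no rate of severe measured values and no rate of reporting, so the size of any shortfall cannot be computed. The percentages in the working rest on assumed per-draw rates, complete draws and two extreme patterns of dependence. The primary endpoint, the secondary efficacy endpoints and the sample size are not affected.

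**What to change.** Add to SAP 12.2.1, on the safety analysis set, a per-subject table of baseline CTCAE v4.0 grade against worst post-baseline grade. State that all scheduled and unscheduled results after the first dose are used. Keep the by-visit summaries.

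Coverage, to be confirmed against the CTCAE v4.0 text:

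- parameters whose Grade 3-4 limits are absolute values: haemoglobin, neutrophils, lymphocytes, platelets, WBC, gradable electrolytes, glucose and albumin;
- AST, ALT and creatinine by site upper limit of normal, which the exclusion criteria already use;
- ALP, bilirubin and APTT where site ranges are available.

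The cost is one derivation and one table family. The results themselves are already collected under Protocol 6.11.2. The exclusion criteria use site limits for only three parameters, and the documents do not say that ranges for the others are collected, so those may have to be obtained from sites. SAP Section 1 allows revision that makes the data more credible and useful, and Protocol 9.4.6 allows additional analyses with details in the SAP. The change should be made before the data are fixed for analysis.

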12.2.2 Neurological and Mental Status Assessments

Neurological and mental status will be summarized in shift tables by time point according to following items.

- Presence of finding of cranial nerve abnormalities
- Presence of finding of sensory abnormalities
- Presence of finding of motor abnormalities
- Presence of finding of coordination (gait) abnormalities
- Presence of finding of reflex abnormalities
- Presence of finding of mental status abnormalities

12.2.3 Summary of Vital Sign Parameters

Descriptive statistics of following vital sign parameters will be calculated by time point for both of measured

values and changes from baseline.

- Systolic/Diastolic blood pressure (mmHg)
- Pulse rate (beats/minute)
- Temperature (°C)
- Percutaneous arterial oxygen saturation (SaO₂) by a pulse oximeter (%)

12.2.4 Summary of ECG Parameters

Descriptive statistics of following ECG test parameters will be calculated by time point for measured values.

- Heart rate (/minute)
- RR interval (msec)
- QRS interval (msec)
- PR interval (msec)
- QT interval (msec)
- Fridericia corrected QT interval (QTcF) (msec)

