An extensive electrocardiogram (ECG) assessment in two clinical studies conducted respectively in Japan and Korea demonstrated that there was no drug-concentration-dependent nor treatment-duration-dependent change in Fridericia-corrected QT interval (QTcF) and there was no significant relationship between the plasma drug (arsenic) concentration of darinaparsin and a change in QTcF interval from time-matched baseline.

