3.2.1. Laboratory Test Values

- (1) Patient with inadequately maintained major organ functions as evidenced by the following laboratory test values taken at the screening visit. These laboratory test values should not be affected by blood transfusion or administration of hematopoietic growth factor agents, etc. Even though the patients who meet none of the following

criteria, subject's condition should not show an obvious tendency toward worsening as determined by the principal investigator or sub-investigator:

- Electrocardiogram (ECG): Fridericia-corrected QT interval (QTcF) \geq 450 msec;
 - Hemoglobin: $<$ 8.0 g/dL;
 - Neutrophil count: $<$ 1,000/mm³;
 - Platelet count: $<$ 50,000/mm³;
 - Aspartate aminotransferase (AST) and alanine aminotransferase (ALT):
> 3 times ULN defined at the investigational site; or
 - Creatinine: > 1.5 times ULN defined at the investigational site;
- (2) Patients with a positive result for either hepatitis C virus antibody (HCV antibody) or hepatitis B virus (HBV) surface antigen (HBs antigen) test during the screening period. Alternatively, the patients with a negative result for HBs antigen; however, with a positive result for either HBV surface antibody (HBs antibody) or HBV core antibody (HBc antibody), and with an HBV deoxyribonucleic acid (DNA) level (HBV-DNA level) \geq the detection sensitivity of the assay;
- (3) Patients who are known to be positive for human immunodeficiency virus antibody (HIV antibody) or human T-cell leukemia virus type I antibody (HTLV-1 antibody);

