12.2.4	Summary of ECG Parameters	16
12.2.5	Summary of PK Parameters	16
13	LISTING.....	17

Abbreviations and Terms

List of Abbreviations

Abbreviation	Definition
AE	Adverse Event
AESI	Adverse Event of Special Interest
AITL	Angioimmunoblastic T-cell Lymphoma
ALCL	Anaplastic Large Cell Lymphoma
BSA	Body Surface Area
CI	Confidence Interval
CR	Complete Response
DCR	Disease Control Rate
DOR	Duration of Response
ECG	Electrocardiogram
eCRF	electronic Case Report Form
FAS	Full Analysis Set
IPI	International Prognostic Index
NCI-CTCAE	National Cancer Institute Common Terminology Criteria for Adverse Events
ORR	Overall Response Rate
OS	Overall Survival
PFS	Progression-Free Survival
PIT	Prognostic Index for T-cell lymphoma
PD	Progressive Disease
PK	Pharmacokinetics
PKS	Pharmacokinetics Analysis Set
PPS	Per Protocol Set
PR	Partial Response
PTCL	Peripheral T-cell Lymphoma
PTCL-NOS	PTCL-not otherwise specified
RD	Relapsed Disease
SAF	Safety Analysis Set
SAP	Statistical Analysis Plan
SD	Standard Deviation
SD	Stable Disease
TTR	Time to Response

List of Terms

Term	Definition
SP-02	Drug substance code of Darinaparsin
SP-02L	Product code of Darinaparsin for injection
Day 1	The first day of 5 consecutive days of investigational drug administration in each cycle; including the case that the planned dosing on the first day is skipped
First screening visit	The day at which the subject signs the informed consent
Screening period	The period from the day of the first screening visit to the day before the first day of Cycle 1 (Day 1 of Cycle 1)
Treatment period	The period from the first day of Cycle 1 (Day 1 of Cycle 1) to the day before the first examination, observation and investigation scheduled during the follow-up period
Follow-up period	The period from the day of the first examination, observation and investigation scheduled during the follow-up period to the day of the last examination, observation and investigation scheduled during the follow-up period (including follow-up adverse event assessment)
Study period	Period consisting of screening period, treatment period and follow-up
Baseline	Results at the last time point of examination, observation and investigation before the start of the first administration of investigational drug in Cycle 1
Tumor response	“Complete Response (CR)” and “Partial Response (PR)”
Overall Response Rate	Proportion of subjects with “CR or PR” in the evaluable subject population

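### SAP 12.2.4 summarises ECG parameters as measured values only, so the planned tables omit the within-subject QTcF change that laboratory values and vital signs receive

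*SAP*

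**What the plan says.** SAP 12.2.4 covers heart rate, RR, QRS, PR, QT and QTcF: "Descriptive statistics of following ECG test parameters will be calculated by time point for measured values". Change from baseline is not mentioned.

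The two neighbouring sections do more. SAP 12.2.1 says laboratory parameters "will be calculated by time point for both of measured values and changes from baseline". SAP 12.2.3 begins "Descriptive statistics of following vital sign parameters will be calculated by time point for both of measured", and the sentence continues over the page break to include changes from baseline.

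Protocol 9.4.4 puts the three domains in one sentence: "Vital signs, laboratory values and ECG parameters will be summarized by item and time point". SAP 7.4 lists one departure from the protocol, the age cut-off, and nothing about ECG.

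The statistics for a continuous variable are given in SAP 7.2: "Number of available data, Mean, Standard deviation (SD), Median, First and third quartile points, Minimum and Maximum". Baseline is defined in the SAP list of terms: "Results at the last time point of examination, observation and investigation before the start of the first administration of investigational drug in Cycle 1".

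Protocol 6.10, Table 4, schedules ECGs at screening, before and after the Day 1 infusion, before and after the Day 5 infusion in Cycle 1 only, on Day 8, and on Day 22 in follow-up.

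**The concern.** For QTcF, the useful safety quantity is how far a subject moved from his or her own pre-treatment value. The documents treat QTcF as worth watching. It is an exclusion criterion (Protocol 3.2.1), congenital long QT syndrome is another (3.2.2), and ECGs bracket the infusion. The phase 1 assessment described in Protocol 1.2.4 looked at "a change in QTcF interval from time-matched baseline". Yet ECG is the one numeric safety domain in SAP 12.2 without a change summary.

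No other table supplies it. The shift tables in SAP 12.2.2 are for neurological and mental status. The events of special interest in 12.1.6 are psychiatric, nervous system and hepatobiliary. ECG otherwise appears only in the listings (SAP 13).

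At stake is the readability of a descriptive safety table: whether it shows the size and spread of QTcF change, and whether later-cycle figures can be interpreted once subjects have left.

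**Working it through.** The documents state no QTcF SD, correlation or precision target, so there is no plan figure to reproduce. The check compares the texts and then adds an illustration.

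**1. What each section delivers**

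| Domain | SAP section | Measured values | Change from baseline |
|---|---|---|---|
| Laboratory | 12.2.1 | yes | yes |
| Vital signs | 12.2.3 | yes | yes |
| ECG | 12.2.4 | yes | no |

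Baseline is defined and repeat ECGs are collected, so the missing column can be derived from planned data.

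**2. What a rise can look like in the planned table.** A subject going from 380 to 445 msec has risen by 445 − 380 = 65 msec. The later value is below 450 msec and need not be the maximum at its time point, so the summary table need not reveal it.

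**3. Later cycles.** No imputation is planned (Protocol 9.4, SAP 8.2.2). Let *f* be the fraction still present, and let B_stay and B_leave be the baseline means of those who stay and those who leave. Then

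raw later mean − raw baseline mean = mean change among stayers + (1 − *f*)(B_stay − B_leave).

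The second term is not a drug effect. If 30 of 65 remain (an assumption), it equals 35/65 = 0.54 of the baseline difference between the groups. Change from baseline removes this term. It does not remove selection on the change itself, because the mean still covers only those who stayed.

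**4. Precision when the same subjects are present.** With complete data, the mean change equals the difference of the two time-point means. What the planned table lacks is the SD of the change, so a reader would have to treat the two means as unpaired.

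- Paired: SE = SD × √(2(1 − ρ)/n)
- From two time-point means: SE = SD × √(2/n)
- Ratio of the second to the first: 1/√(1 − ρ), whatever the SD and n

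Inputs: n = 65, the planned sample size (Protocol 9.2), because SAP 12 analyses ECG on the safety set. SD and ρ are assumed.

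At SD 20 msec and ρ = 0.7:

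- Paired: 20 × √(0.6/65) = 1.92; × 1.96 = 3.8 msec
- Two means: 20 × √(2/65) = 3.51; × 1.96 = 6.9 msec

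95% half-widths (msec) over the assumed range:

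| SD | Two means | Paired, ρ = 0.5 | Paired, ρ = 0.7 | Paired, ρ = 0.8 |
|---|---|---|---|---|
| 15 | 5.2 | 3.6 | 2.8 | 2.3 |
| 20 | 6.9 | 4.9 | 3.8 | 3.1 |
| 25 | 8.6 | 6.1 | 4.7 | 3.8 |

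The ratio is 1/√0.5 = 1.4 at ρ = 0.5 and 1/√0.2 = 2.2 at ρ = 0.8.

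**5. The 450 msec limit.** Protocol 3.2.1 applies it to the screening ECG, which may be taken on any day from Day -28 to Day -1. Baseline is the last pre-dose value, normally the Day 1 pre-infusion ECG, and no text re-applies the limit there.

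**The case against.** The strongest reply is that nothing has been broken. Protocol 9.4.4 asks only for a summary by item and time point, and SAP 12.2.4 gives one. That stands: a reader might infer a conflict between SAP and protocol from the uneven treatment, but the protocol does not promise change from baseline for any of the three domains.

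A reader might also infer that QTcF prolongations would go unnoticed. The documents do not support that. The maximum at each time point is reported (SAP 7.2), ECGs are listed by subject (SAP 13), and investigators must check each subject's ECG change from baseline and report clinically significant changes as adverse events (Protocol 7.1.1). What stays out of the tables is a rise that remains within the observed range and is not judged clinically significant.

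A third tempting reading is that every subject enters below 450 msec, so any later value at or above it must be new. That fails too, because the Day 1 pre-dose value could already be at or above the limit. The safety set also keeps any dosed subject later found ineligible (Protocol 4.4.2, SAP 5.2).

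Finally, the phase 1 assessment found no concentration- or duration-dependent QTcF change (Protocol 1.2.4), which is an argument for a lighter analysis here. Its time-matched method cannot simply be copied, since Table 4 has no time-matched baseline series. Both points hold, and they limit how much should be asked for. They do not explain why a simple change column was left out for ECG alone.

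**Conclusion.** The point holds as a minor gap in the safety tables. The planned ECG tables give no within-subject QTcF change, and their later-cycle means are affected by which subjects remain.

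The texts alone establish this. The half-widths are only a yardstick for the information lost: the SAP plans no confidence interval or test for ECG, and the SD and correlation are assumptions. On those assumptions, uncertainty about a mean shift is 1.4 to 2.2 times wider without the pairing. The half-widths use the same 65 subjects at both time points, so they do not measure the effect of drop-out. Change from baseline would lessen that problem but not cure it.

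**What to change.** In SAP 12.2.4, summarise change from baseline alongside measured values for every ECG parameter, using the SAP's baseline definition, as 12.2.1 and 12.2.3 already do. Add QTcF change from before to after infusion on Day 1 of each cycle and on Day 5 of Cycle 1. On Cycle 1 Day 1 this will normally coincide with change from baseline; at the other visits it is additional.

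A count of subjects with a post-dose QTcF at or above 450 msec is optional. If added, show it by baseline status (below the limit, or at or above it), because the limit applies only to the screening ECG. This is a reporting category and has no bearing on patient management.

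The cost is a change of SAP wording, added columns and a short QTcF table. All the data are already collected under Protocol 6.10, so this is a free improvement.
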